#### 2.9. Blinding and Masking

If eligible, baseline assessments will be carried out on site at time of recruitment or at home, as per the participant's preference. The baseline assessment will be accessed by a secure link sent via REDCap™, which participants will be asked to complete before their first treatment session. Once baseline is completed, the participants will be randomized. The outcome assessments at 3, 6, 12-months post-randomization will also be completed by secure links sent via REDCap™. Participants and providers will not be blind to treatment allocation; however, both will be told that we are evaluating the same intervention and there is clinical equipoise about whether one is better than the other. Outcome measures for participants will be administered through REDCap™. Trained research assistants independent of the treatment delivery and blind to allocation status will conduct the participant interviews and child assessments.

#### 2.10. Economic Evaluation

We will evaluate the cost-effectiveness of non-specialist providers and telemedicine, compared to specialist providers and in-person sessions. We will undertake a cost-utility analysis conducted at the 12-month post-randomization follow-up point. The primary outcome will be quality-adjusted life years (QALYs) calculated using the EuroQol 5 Dimension 5 Level (EQ-5D-5L) measure of health-related quality of life, collected at 3, 6 and 12-months.

- **2.10.1. Economic-related data.** The primary outcome related to the economic evaluation is quality adjusted life years (QALYs) calculated using the EuroQol 5 Dimension 5 Level (EQ-5D-5L) measure of health-related quality of life. An advantage of the EQ-5D-5L is that an overall utility score of health-related quality of life can be obtained, which facilitates comparisons with other interventions and health states in other illnesses.
- **2.10.2. Service use.** The use of all health services, other than the intervention (BA), are being recorded using an adapted version of the health services utilization questionnaire (HSUQ). Data on the use of BA (number and duration of therapy contacts and with whom) will be collected from existing clinical records. This measure (*see Health Service Utilization Questionnaire, Appendix C Study Measures*, pg. 35) was adapted with reference to other measures used in perinatal depression populations and for use in Canadian and US contexts with input from service users and clinicians. It will be completed at baseline (covering the last 3 months) and each follow-up interview (covering the period since the last interview). The HSUQ records use of health services, specifically: hospital inpatient stays,

outpatient appointments, emergency department visits and ambulance contacts, and community health contacts.

**2.10.3. Costs.** BA will be directly costed for each comparison taking a standard micro-costing approach. Unit costs for BA will include all employer costs and appropriate overheads (capital, managerial, administrative etc.; *see List of Costs, Appendix C – Study Measures,* pg. 108). The cost of supervision will be included and the time each therapist spends on various direct and indirect participant-related activities (non-participant contact time including, for example, training, administration, meetings with other professionals etc.) will be estimated using a questionnaire. Data on the use of all other health services will be costed for each individual participant over the course of the trial. Unit costs in both Canada and the USA will be obtained from Canadian guidelines on person-level costing and local Medicaid, Medicare, and private insurer fee schedules commonly available in the US, respectively.

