# 2.5. Outcomes and Timing of Assessments.

# Table 6. Outcomes

Study Variable	Instrument	Outcome (Range)
Maternal: Measured at Baselin	e and 3*-, 6- and 12-months post-randomization	
Maternal Characteristics**	Trial Baseline Questionnaire 53,54	Self-reported age, education level, marital status, immigrant status and ethnicity, clinical history with depression or anxiety (severity, chronicity, number of prior episodes, and age at first episode, occupational status, number of children, pregnancy intention, pregnancy history, delivery and birth, sexual orientation.
Depressive Symptoms	Edinburgh Postnatal Depression Scale (EPDS)41	Mean continuous score of a 10-item scale (0-30)
Anxiety Symptoms	Generalized Anxiety Disorder Scale (GAD-7)42	Mean continuous score of a 7-item scale (0-21)
Response & Remission	Patient Health Questionnaire-9 (PHQ-9) 	Response: PHQ<10 Remission is defined as PHQ<5
Perceived Support	Multidimensional Scale of Perceived Social Support 	Mean continuous score of a 12-item scale (1-84)
Disability Assessment	World Health Organization Disability Assessment Schedule (WHODAS) 	Mean continuous score of a 12-item scale (0 – 48)
Quality of Life Assessment	EQ5D-5 Level (EQ5D-5L) 	Mean continuous score of a 5-item scale (1-25)
Trauma Symptoms	Abbreviated PTSD Checklist (PCL-6) 	Mean continuous score of a 6-item scale (1-30)
Patient-Reported Activation	Premium Abbreviated Activation Scale 	Mean continuous score of a 5-item scale (0-20)
Patient Satisfaction***	Client Satisfaction Questionnaire-8 (CSQ-8)61	Mean continuous score of an 8-item scale (1-32)
Therapeutic Alliance***	Working Alliance Inventory-Short Revise (WAI-SR)62	Mean continuous score of a 12-item scale (1-60)
Health Service Utilization	Health Service Utilization Form 	3, 6 months - Total score of a 16-item scale (0-32); 12 months – Total score of a 19-item scale (0 – 38)
Treatment Preference**	Delivery of treatment and treatment provider preference	Score of 0 or 1
COVID-19 Exposure	1-item question on COVID-19 exposure	Self-reported
Health Benefits Access and Use	2-item question on access and use of health benefits	Self-reported Self-reported
Sexual Orientation o	2-item question on sexual orientation	Self-reported
Home Visit Survey □	4-item question on home visit perspective	Self-reported

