#### 2.6. Sample Size

The primary outcome measure will be participant's EPDS mean score at 3 months after randomization; the assessment period will be extended in the event that there is a hiatus to treatment due to significant perinatal-related life events (e.g., giving birth, obstetrical complications, COVID-19) or to one week after the last session if participants complete treatment after the 3 month-post randomization period. The study is designed to be a noninferiority trial with four arms: telemedicine specialist, telemedicine non-specialist, in-person specialist, in-person non-specialist. The two primary hypotheses are that telemedicine will be non-inferior to in-person, and that non-specialist delivery agents will be non-inferior to specialist delivery agents. The sample size calculation is based on an EPDS mean estimate of 7.93 (SD=4.68). Using a non-inferiority margin of 10% (i.e., EPDS score of 0.79) in relation to the mean), and an alpha=0.05 for our first comparison (NSP vs. SP) we require 431 participants in each of the two groups to provide greater than 80% power. To account for 10% drop out, the sample size is inflated to N=958 (479 per group, NSP vs. SP). Using a non-inferiority margin of 13% (i.e., EPDS score of 1.03 in relation to the mean), and an alpha=0.05 for our second comparison (TM vs. IP), we require an additional 268 IP participants. When combined with the 958 TM participants, this yields a total study sample size of N=1,226 which accounts for 10% loss to follow-up. Previous randomized non-inferiority trials have demonstrated that a 14% non-inferiority margin can be considered clinically meaningful.

We are planning a final sample size of N=1,230, four more participants than the power calculation requires. The reason for this n=4 over recruitment, is to provide flexibility due to the fact that we do not receive each site's recruitment numbers until the end of each day. These statistics have been reviewed and approved by our study statistician.

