- **3.5.5.1. Cost-effectiveness analyses.** The primary economic evaluation will be a cost-utility analysis (a cost-effectiveness analysis where outcomes are measured using a utility measure) carried out at the 12-month post-randomization follow-up point with outcomes expressed in terms of QALYs based on cases with non-missing data. Costs and outcomes will be compared at 12 months and will be presented as mean values by arm with standard deviations. Mean differences and 95% confidence intervals will be obtained by non-parametric bootstrap regressions to account for the non-normal distribution of the data. A secondary analysis will be a cost-effectiveness analysis using the primary clinical outcome measure, the EPDS at 12-months post-randomization. Cost-effectiveness will be assessed using the net benefit approach with reference to Bosmans' methods for economic evaluations alongside

equivalence or noninferiority trials. Incremental cost-effectiveness ratios (ICERs) will be calculated, defined as the mean difference in cost between two groups divided by the mean difference in effect. Uncertainty will be explored using cost-effectiveness planes and cost-effectiveness acceptability curves (CEACs) based on the net-benefit approach. Cost-effectiveness planes illustrate the uncertainty around the estimates of costs and effects by plotting the bootstrapped cost and effects, with points in each quadrant indicating a different implication for economic evaluation. CEACs are an alternative to confidence intervals around ICERs and show the probability that one intervention is cost-effective compared to another, for a range of values that a decision maker would be willing to pay for a unit improvement in the outcome of interest.

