1.4. Outcome Assessments

We used the following definitions to define outcomes^{2, 3}:

- Primary Outcome:** the main outcomes of interest for the SUMMIT trial.
- Secondary Outcome:** any outcome that is not a primary outcome but supports the primary outcome by corroborating results or by explaining a mechanism (mediators and moderators).
- Exploratory Outcome:** variables of interest which can serve as a basis for new directions but may not be relevant to the primary outcome or differ between the treatment arms.

[†]Pregnant and postpartum women refer to women and other persons who are pregnant or postpartum.

Outcome data will be collected at 3-, 6- and 12-months post randomization and 6-24 months post childbirth. [Table 2](#) lists primary and secondary outcomes and their assessment points. All measures proposed in the current study have been previously used and validated in one or more of the investigators' trials and selected because of their potential role in the presumed causal pathway ([Figure 3](#)). Our emphasis on mothers' self-reported data adheres to PCORI's methodology standards⁴ that emphasize that the patient population is the best source of information.

Additionally, to address the aim of conducting a process evaluation, qualitative data is collected throughout the phases of the trial from perinatal participants, significant others, treatment providers, clinical leads, and stakeholders.

Due to the COVID-19 pandemic, and in line with our published study protocol¹, several measures were added at various assessment points following the start of data collection. These include:

- **treatment preference** (TM or IP; added April 6, 2020, n=30 missed* the measure at baseline; 2.4% of final sample size),
- **trauma symptoms** (PCL-6; added April 6, 2020, n=30 missed* the measure at baseline; 2.4% of final sample size),
- **quality of life** (EQ-5D5L; added April 6, 2020, n=30 missed* the measure at baseline; 2.4% of final sample size), and
- **COVID-19 exposure** (added June 26, 2020, n=170 missed* the measure at baseline; 13.9% of final sample size).

[figure not shown]
*Note: Multiple imputation methods will be used to impute missing data and compare model results to the complete case analysis. See [Missing Data and Imputation](#).

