1.5. Randomization

All SUMMIT participants are stratified by perinatal period (antenatal vs. postnatal) and were initially (Phase 1) randomized within site to one of four arms (see [Figure 2](#)). However, during the early part of the COVID-19 pandemic (Phase 2) when in-person care was prohibited, participants were randomized to only one of two arms: TM NSP and TM SP ([Figure 2](#)). All sites resumed randomization to all 4 arms 16 months later (Phase 3). Given that Phase 2 consisted of

Figure 2. Randomization strategy

*Randomization can shift to the two telemedicine arms based on site specific, COVID-related institutional restrictions, and once enrollment to in-person arms is complete.

randomizing participants exclusively to TM, there was an imbalance in participant assignment between the IP and TM arms. To address this, a weighted randomization approach (3:1, favoring IP) was used in Phase 3 in which a reduced percentage of

participants were randomized to the TM arms to ensure that the study's sample size targets will be met, and the final sample has an equal number of IP and TM participants. Due to the Omicron wave in December 2021 and January 2022, participants were randomized to TM-only again and randomization switched back to a 1:1 ratio. However, sites were permitted to switch between a 1:1 TM-only (2 arm) and a 1:1:1:1 both TM and IP (4 arm) randomization scheme based on site-specific COVID restrictions and Infection Prevention and Control (IPAC) recommendations. Sites began resuming Phase 1 randomization to IP in the 1:1:1:1 ratio in January 2022, and all sites returned to Phase 1 randomization by April 2022. Randomization to all 4 arms will be followed until in-person arms are fully enrolled after which randomization 1:1 to the two telemedicine arms will be followed.

Table 2: SUMMIT Outcomes (A more detailed list can be found in [Appendix 1](#)).

Study Variable	Instrument	Outcome (Range)
Maternal: Measured at Baseline and 3*-, 6*- and 12*-months post-randomization		
Maternal Characteristics**	Trial Baseline Questionnaire ^{6,7}	Self-reported age, education level, gender identity and sexual orientation, marital status, immigrant status and ethnicity, clinical history with depression or anxiety (severity, chronicity, number of prior episodes, and age at first episode), occupational status, number of children, pregnancy intention, pregnancy history, delivery and birth.

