Appendix 1. List of Variables

VARIABLE	MEASURE	TIME OF ASSESSMENT						
		SCREENING	BASELINE	SESSION-WISE	3 MONTHS	6 MONTHS	12 MONTHS	HOME VISIT
PRIMARY OUTCOME								
Depressive symptoms	Edinburgh Postnatal Depression Scale (EPDS)							
SECONDARY OUTCOMES								
Depressive symptoms	Edinburgh Postnatal Depression Scale (EPDS)							
Anxiety Symptoms	General Anxiety Disorder-7 (GAD-7)							
Child Mental Development	Bayley-IV							
Psychosocial Stimulation	Home Observation Measurement Evaluation (HOME)							
EXPLORATORY OUTCOMES								
Response & Remission	Patient Health Questionnaire (PHQ-9)							
Suicide Risk*	Columbia Suicide Severity Risk Screener (C-SSRS)							
Patient-Reported Activation	Premium Abbreviated Activation Scale (PAAS)							
Quality of Life Assessment	EQ5D-5-level (EQ5D-5L)							

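### The 12-month QALY is defined without the baseline EQ-5D-5L that the trial collects, and the cost-utility regressions name no baseline-utility covariate

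*Protocol*

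**What the plan says.** Protocol 2.10 plans a cost-utility analysis at 12 months. Its primary outcome is the QALY, calculated from EQ-5D-5L "collected at 3, 6 and 12-months". Baseline is not listed there, although 2.10.2 does name baseline for the service-use questionnaire.

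The measurement schedules differ from 2.10. Protocol Table 6 puts EQ-5D-5L in the maternal block measured at baseline, 3, 6 and 12 months, and no footnote exempts it from baseline. SAP Table 2 places it under "Maternal: Measured at Baseline and 3*-, 6*- and 12*-months post-randomization". SAP Appendix 1 ticks baseline, 3, 6 and 12 months. SAP 1.4 records the late start: "EQ-5D5L; added April 6, 2020, n=30 missed* the measure at baseline; 2.4% of final sample size".

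Protocol 3.5.5.1 expresses outcomes as "QALYs based on cases with non-missing data" and obtains mean differences and intervals from non-parametric bootstrap regressions. The only reason given for the bootstrap is non-normal data, and no covariate is named. Section 3.5.6.2 adds a chained-equation imputation re-run of the cost-effectiveness analyses and a comparison of included women with the full sample. Section 3.5.6 adds retrospective access to health records for service use and costs.

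The baseline-imbalance rules (Protocol 3.5.1, SAP 3.4.1) are written for the clinical EPDS analyses. The SAP has no economic section that extends them.

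**The concern.** A QALY over 12 months is an area under the utility curve that starts at randomization. With measurements at 3, 6 and 12 months only, the first quarter of that area has no left-hand point. The analyst must then drop it, carry a value backwards or bring in baseline. The text does not say which.

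Utility measured later depends on utility at entry, so a difference between groups at baseline persists into the follow-up values. This holds whether or not the baseline point is counted in the area. Protocol 1.5 hypothesizes equal effectiveness at lower cost, so the QALY difference is expected to be close to zero, and a small carried-over difference is then large relative to the quantity being estimated.

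The two comparisons differ. Provider type was randomized in every phase, so only chance imbalance is at issue there. Telemedicine and in-person groups are partly non-concurrent, because allocation was telemedicine-only for part of the pandemic (Protocol 2.2.3.2, SAP 1.5). Their baseline utilities could therefore differ for reasons other than chance.

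**Working it through.** **Stated figure.** SAP 1.4 gives 30 women without baseline EQ-5D-5L, 2.4% of the final sample. The SAP sample size is 1,226; Protocol 2.6 says "We are planning a final sample size of N=1,230, four more participants than the power calculation requires".

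- 30 / 1,226 = 2.45%
- 30 / 1,230 = 2.44%

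Both round to the stated 2.4%, so baseline utility should be obtainable from about 97.6% of the sample.

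**Area weights.** With times 0, 0.25, 0.5 and 1 year and the trapezoidal rule, each interval contributes half its length to each end.

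- Baseline: 0.25/2 = 0.125
- 3 months: 0.25/2 + 0.25/2 = 0.25
- 6 months: 0.25/2 + 0.5/2 = 0.375
- 12 months: 0.5/2 = 0.25
- Sum: 1.0 year

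With 3, 6 and 12 months only, the weights are 0.125, 0.375 and 0.25, which sum to 0.75 year. The missing 0.25 year is months 0 to 3.

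**Shift from a baseline difference.** Let d be the baseline utility gap between groups and b the slope of later utility on baseline utility, taken as equal at all three waves. The documents give neither, so these are assumptions: d from 0.01 to 0.05 and b from 0.3 to 0.7. With no true effect and no adjustment:

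- Months 3 to 12 only: shift = d × b × 0.75
- Baseline included in the area: shift = d × (0.125 + b × 0.875)

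| d | b | Months 3–12 only | From baseline |
|---|---|---|---|
| 0.01 | 0.3 | 0.0023 | 0.0039 |
| 0.02 | 0.5 | 0.0075 | 0.0113 |
| 0.05 | 0.7 | 0.0263 | 0.0369 |

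Adding the baseline point without adjusting makes the shift larger. The area definition and the covariate therefore belong together. Adjusting for baseline utility removes this shift in expectation.

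**How large a gap could chance produce?** Assume a utility SD of 0.15 to 0.25 (not in the documents). The 95% half-width of the baseline difference is 1.96 × SD × √(1/n₁ + 1/n₂).

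- 615 vs 615 (half of 1,230 each): 0.017 to 0.028
- 958 vs 268 (the telemedicine and in-person numbers in SAP Table 5): 0.020 to 0.034

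A gap of 0.05 is outside both ranges, so the top of the table needs something beyond ordinary chance. With chance alone and b = 0.7, the largest shifts from baseline are 0.028 × 0.7375 = 0.021 QALY for provider and 0.034 × 0.7375 = 0.025 for mode. Over months 3 to 12 they are 0.028 × 0.525 = 0.015 and 0.034 × 0.525 = 0.018.

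**Complete cases.** Protocol 3.2 expects 20% loss and regards 12-month follow-up of at least 80% as realistic. At 20%, 0.8 × 1,230 = 984 women remain, fewer if another wave or a cost item is missing.

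**The case against.** The strongest reply is that the omission is one loose sentence. Three schedules list EQ-5D-5L at baseline, and SAP 1.4 says missing values on the late-added measures will be imputed, so the baseline value is evidently meant for use. Section 2.10 may simply list the follow-up waves. A bootstrap regression can also carry covariates, and the Protocol does not exclude baseline utility. This stands in part. It rules out a reading that baseline utility was not collected, or that adjustment was rejected by design. What remains is an inconsistency between 2.10 and the schedules and a choice affecting the result that neither document fixes in advance.

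A second reply is that chance imbalance under randomization is not systematic bias, and that the planned intervals, planes and acceptability curves already display the uncertainty. That is fair for provider type, where the gain from adjustment is precision and protection against the imbalance that actually occurs. It is less complete for telemedicine versus in-person, where part of the baseline difference may come from calendar time.

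Third, a reader might infer that dropout is ignored, or that at least 20% of women leave the main analysis. The documents do not support either. The at-least figure in Protocol 3.2 is 80% follow-up, so expected loss is up to about 20%, and SAP Table 4 notes dropout below 10% at 3 months. The imputation re-run, the included-versus-full comparison and the record access address missing data in part. Whether imputation or complete cases is called the base case mostly relabels two analyses that are both planned.

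**Conclusion.** The point holds as an internal inconsistency and an unspecified adjustment in a secondary economic analysis. The QALY definition leaves out a baseline measurement that the trial schedules and that only about 2.4% of women missed through its late addition. No text commits the analyst to adjusting for it.

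The size rests on assumed baseline gaps (0.01 to 0.05) and slopes (0.3 to 0.7): about 0.002 to 0.026 QALY over months 3 to 12, or 0.004 to 0.037 with baseline in the area and no adjustment. The upper ends need a gap larger than chance would usually give under the assumed SDs.

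It would be tempting to conclude that cost-effectiveness will be driven by baseline imbalance, or that imbalance decides the net benefit. The documents do not show this. They give no utility data and no willingness-to-pay value, and net benefit also depends on cost, which is hypothesized to be lower. The supportable statement is that the QALY difference could be influenced by an amount that matters when the expected difference is near zero. Neither primary non-inferiority conclusion is touched.

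**What to change.** - Align Protocol 2.10 with Table 6, SAP Table 2 and SAP Appendix 1, so that EQ-5D-5L is listed at baseline, 3, 6 and 12 months.
- Define the QALY as the area under the utility curve through those four points.
- Name baseline EQ-5D-5L utility as a covariate in the bootstrap regressions for both comparisons. For telemedicine versus in-person this removes only the part of any non-concurrent difference that runs through baseline utility.
- State that the roughly 30 missing baseline values will be imputed, so that these women are not dropped. This needs saying: 2.4% is below the 20% trigger in Protocol 3.5.6, and the economic imputation in 3.5.6.2 mentions total costs and outcomes but not baseline utility. The measure was added on April 6, 2020, so these are the earliest recruits.

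Making chained-equation imputation the base case, with complete cases as the sensitivity analysis, is optional and not needed for this point.

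The cost is a few sentences in the Protocol or in an economic analysis plan, plus one added model term. No new data are required. The wording should be fixed before QALYs are compared by arm.
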